Once enrolled, subjects in the experimental group will be prescribed mupirocin 2% ointment and chlorhexidine wash. Instructions for decolonization will be provided to the subjects in a "pre-procedure handout and a medication log in order to help them perform and track the decolonization protocol sufficiently. Subjects in the experimental group will follow decolonization procedures for 5 days prior to surgery.

On the day of their procedure, all subjects will be asked to fill out a demographic survey to evaluate their risk of developing infection. The demographic survey sheet will record the patients' age, sex, prior *Staphylococcus aureus* infections, medications, BMI over 25, smoking status, number of showers per week, and medical history of diabetes, immunosuppression, peripheral vascular disease, and nutritional deficiency. Patients' answers will be recorded in a protected, unidentified database.

Following surgery, all subjects will be asked to send in a picture of their surgical site during the postoperative period at weeks 2 and 4. Patients will submit photos of their surgical site via the Cooper RedCap system. They will receive an email prompting them to upload their photos at these points. Photographs will be evaluated by a study physician upon receipt. After that one month, the patient will be informed that they no longer need to send in any more photos.

Any patient who develops symptoms of an infection or has concerning findings on the pictures will be instructed to schedule a follow up appointment for evaluation. At this visit, their wound will be swabbed for the causative pathogens. The results from the wound culture will be shared with the patients and, if positive for pathogenic bacterial growth, will be started on antibiotics for treatment of their surgical site infection.

Subjects that do not require a follow up appointment will be followed up with a call at one month post-surgery. We will ask these patients if they developed a wound infection or if they had any issues with their surgical site.

C.2. Study Visits

On the day of the procedure, the patient will be given an envelope containing a hard copy of their official consent form to sign (if they did not bring their copy from home) and a demographic survey sheet.

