All patients enrolled in the study, regardless of group, , will send in a picture of their surgical site 2 weeks and 4 weeks after their surgery. Any patient who develops symptoms of an infection or has concerning findings on the pictures they send in will be instructed to schedule a follow up appointment for evaluation. Here, their wound will be swabbed for the causative pathogens.

Any subject who develops an infection will be identified by the pictures sent to the physician or the patients' concern for infection. During this visit, a wound culture will be collected to determine the responsible pathogen. Wound culture results will be recorded within the data collection sheet.

All patients that do not develop an infection will be followed up with a call at one month. We will ask these patients if they developed a wound infection or if they had any issues with their surgical site.

C.3. Study Duration

Subjects will be asked to participate in this study for 1 month after their surgery. The overall study should take a little over a month for the treatment group since they will also have to pretreat the surgical site.

C.4. Drugs, Biologics, and Devices

All drugs used on this study are FDA approved and will be used according to label. The research is not intended to be reported to the FDA as a well-controlled study in support of a new indication for use for the drugs, nor is it intended to support a significant change in the labeling for the drugs.

Mupirocin 2% ointment: Indicated for the eradication of nasal colonization with methicillin-resistant *Staphylococcus aureus* (MRSA) in adult and pediatric patients (aged 12 years and older) and healthcare workers as part of a comprehensive infection control program to reduce the risk of infection among patients at high risk of MRSA infection during institutional outbreaks of infections with this microorganism.

Clorhexidine wash: Indicated for use as an antimicrobial skin cleanser helps reduce bacteria that potentially can cause disease; for skin wound and general skin cleansing; surgical hand scrub; personnel hand wash; and preoperative skin preparation.

C.5. Safety Evaluation (if applicable)

In the case that an infection develops at the surgical site, a bacterial culture will be taken to identify the causative pathogen. This will allow the physician to properly treat the infection with appropriate antibiotics.

C.6. How Participation Differs from Standard-of-Care

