D.6.1. Minimizing Risks

The following is being done to minimize the above risks from occurring:

1. Patients can decline to answer any of the questions on the questionnaire or withdraw from the study at any point.
2. All patients will receive treatment if they develop skin infections.
3. All measures will be taken to avoid breach of PHI. All personal health information will be de-identified from the study data. All data will be stored on a password-protected computer that will not leave the Cooper Center for Dermatologic Surgery. Only study personnel will have access to the computer.
4. All patients will be provided with a telephone number that will allow them to reach a physician in our practice should they have any questions or develop symptoms concerning for infection. They will be scheduled for an appointment if the evaluating physician is concerned for possible infection. Additionally, all patients enrolled will be contacted directly by study personnel one month after the procedure to evaluate if they had or are currently having any complications at the surgical site.
5. Subjects will be screened to avoid enrollment of a patient who may be sensitive to mupirocin or chlorhexidine.
6. Subjects will be provided instructions on how to properly apply mupirocin and chlorhexidine to reduce skin irritation

D.6.2. Privacy Protections

The patient is under no obligation to discuss their involvement with anyone at the office outside of study personnel. They can schedule appointments without mentioning they are involved in a research study.

D.7. Benefits

There are no direct benefits to patients who are involved in this study. This data has the potential to change the standard of care for patients receiving dermatologic surgeries on the lower extremities healing by second intention. Currently, decolonization is not a standard of care before procedures. By showing this process reduces the rate of post-operative infections, physicians could implement this into their practice, leading to reduced morbidity, improved patient outcomes, and reduced healthcare cost burden from surgical site infections.

E. Safety Monitoring

Data and Safety Monitoring Plan

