All participating sites will be required to submit reports of their adverse events on a quarterly basis. The reports will be reviewed by the Principal investigator, [name]. All participating institutions will adhere to the safety and data monitoring plans of their individual institutions in addition to submitting to Cooper on a quarterly basis.

E.1. Recording of Adverse Events (AEs).

All Adverse Events will be captured on the appropriate case report form (CRF) and reviewed by the Principal Investigator. Information to be collected includes event description, time of onset, clinician's assessment of severity, relationship to study procedures (assessed only by those with the training and authority to make a diagnosis), and time of resolution/stabilization of the event. All AEs occurring while on study will be documented appropriately regardless of relationship. All AEs will be followed to adequate resolution.

Any medical or psychiatric condition that is present at the time that the participant is screened will be considered as baseline and not reported as an AE. However, if the study participant's condition deteriorates at any time during the study, it will be recorded as an AE.

AEs with start dates occurring any time after informed consent is obtained until the conclusion of study participation will be recorded. At each study visit, the investigator will inquire about the occurrence of AE/SAEs since the last visit. Events will be followed for outcome information until resolution or stabilization.

E.2. Relationship of AE to Study.

The relationship of each adverse event to the study procedures should be characterized based on 1) relatedness, 2) expectedness, and 3) severity.

All adverse events (AEs) will have their relationship to study procedures, including the intervention, assessed by an appropriately-trained study clinician based on temporal relationship and their clinical judgment. The Principal Investigator will make a final determination regarding the 1) relatedness, 2) expectedness, and 3) severity of the Adverse Event.

The relatedness of the AE will be assessed as follows:

- Definitely Related – There is clear evidence to suggest a causal relationship, and other possible contributing factors can be ruled out.
- Probably Related – There is evidence to suggest a causal relationship, and the influence of other factors is unlikely.

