
I. Appendix

Screening	Patient will be identified as a potential research subject. Their chart will be flagged for their pre-operative visit..
Pre-operative visit	During their standard pre-operative visit, the physician will inform the patient of the study. If the patient agrees to participate, a link to REDCap or a physical copy of the consent form will be sent to them. Patients will be placed into one of two arms. They will be given instructions on the pre-operative decolonization if they are placed in the experimental group.

Day of procedure	Patient will come in for their procedure. They will fill out the demographic survey and receive a hard copy of their consent form.
Post-operative management	Patients will send a picture of their surgical wound to the physician 2 weeks after and 4 weeks after their procedure. If the patient does not develop any infection, they will be called 1 month after their procedure to check on their progress.
Infection develops	Patients will be asked to report to the office. A swab will be taken of the infection site to test for the causative pathogen. Appropriate treatment will be given when the results are received.

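### The protocol gives three rules for who gets the one-month call, and after surgery it ties active adverse-event inquiry to a visit made only for suspected infection.

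*Protocol*

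**What the plan says.** **Adverse events.** Section E.1 sets the recording window: "AEs with start dates occurring any time after informed consent is obtained until the conclusion of study participation will be recorded". It sets the method of inquiry: "At each study visit, the investigator will inquire about the occurrence of AE/SAEs since the last visit". Section C.3 sets the end of the window: "Subjects will be asked to participate in this study for 1 month after their surgery".

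**Contacts after surgery.** Under C.1, C.2 and the Appendix every patient sends photographs at weeks 2 and 4. An in-person visit follows only on a trigger (C.1): "Any patient who develops symptoms of an infection or has concerning findings on the pictures will be instructed to schedule a follow up appointment".

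**The one-month call.** Four places describe who receives it:

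- C.1: "Subjects that do not require a follow up appointment will be followed up with a call at one month post-surgery".
- C.2: "All patients that do not develop an infection will be followed up with a call at one month".
- Appendix, post-operative row: "If the patient does not develop any infection, they will be called 1 month after their procedure to check on their progress".
- D.6.1, item 4: "all patients enrolled will be contacted directly by study personnel one month after the procedure".

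C.1 and C.2 limit the content of the call to wound infection and problems at the surgical site. D.6.1 limits its contact to complications at that site.

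**The concern.** There are two linked problems.

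First, the rules for the final contact name three different groups of patients. Section A.5 plans 10 centers. One center could follow C.1, another C.2 and a third D.6.1, and each could point to the protocol in support. At stake is an even last contact for all patients, which is also listed in D.6.1 as a protection for them.

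Second, E.1 promises recording to the end of participation and names the study visit as the occasion for asking. After the day of surgery, the only patients with a described visit are those with suspected infection. Infection is the outcome that the intervention is expected to change, so active inquiry about adverse events could differ by arm because of the treatment effect. Controls would be asked more often, which could make the experimental arm look slightly safer than it is.

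**Working it through.** **1. Who is contacted at one month under each rule**

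| Patient | C.1 | C.2 and Appendix | D.6.1 |
|---|---|---|---|
| Never needed an appointment, no infection | named | named | named |
| Seen for suspected infection, found uninfected | not named | named | named |
| Seen and infected | not named | not named | named |

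The rules agree on the first row only. An infected patient is contacted only under D.6.1. A patient seen and found uninfected is missing from C.1.

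**2. Where adverse events are actively asked about**

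- Day of procedure: a visit for all patients in both arms, after the five-day regimen. E.1 applies.
- Weeks 2 and 4: photographs from all patients. No adverse-event question is attached.
- Suspected-infection appointment: a visit for some patients. E.1 applies.
- One-month call: questions on infection and the surgical site only, even under D.6.1.

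So for a patient without suspected infection, no general adverse-event question is specified after the day of surgery.

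**3. How unequal inquiry could be**

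Inputs from A.5: 424 patients per arm, 848 in all; infection rates 10% (control) and 5% (experimental). The protocol states neither alpha nor power. With two-sided 0.05 and 80% power assumed, the arcsine formula reproduces its figure:

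- h = 2·asin(√0.10) − 2·asin(√0.05) = 0.1925
- n = 2(1.960 + 0.842)² / h² = 424 per group

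The sample size is not in dispute and serves only to scale what follows.

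Expected infections are 424 × 0.10 = 42.4 and 424 × 0.05 = 21.2, together 63.6 of 848 (7.5%).

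The protocol gives no number of suspected-infection visits. Assume that every infected patient is seen, and that a fraction u of uninfected patients is also seen, equal in both arms. Then:

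patients seen per arm = 424 × [p + u(1 − p)]

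| u (assumed) | Control | Experimental | Ratio | Share of 848 with no post-operative visit |
|---|---|---|---|---|
| 0 | 42.4 | 21.2 | 2.0 | 784.4 / 848 = 92.5% |
| 0.10 | 42.4 + 38.2 = 80.6 | 21.2 + 40.3 = 61.5 | 1.3 | 706.0 / 848 = 83% |
| 0.20 | 42.4 + 76.3 = 118.7 | 21.2 + 80.6 = 101.8 | 1.2 | 627.5 / 848 = 74% |

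Most patients have no post-operative visit in every row, but the difference between arms shrinks quickly as uninfected patients are seen. Assuming instead a fixed number of patients seen per infection, from 1 to 4, leaves 92.5% to 70% without a visit. That model sets the ratio at 2 by construction, so it is no evidence for a two-fold difference.

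**The case against.** The strongest reply is that other text already covers most of the gap.

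- **The call rules may be compatible.** None of them says that only the named group is called. C.1 and C.2 name subsets of the D.6.1 group, so a center that calls everyone satisfies all of them. That is a possible reading. But if everyone is called, there is no reason for C.1 and C.2 to single out a subset, and a center reading only the procedures section would apply the narrower rule.
- **A reader might infer that later infections will be missed.** The text does not support that. A patient seen at week 2 and found uninfected still sends the week-4 photograph, which a study physician reviews, and has a telephone line under D.6.1. An infected patient who is not called has already been identified as infected. What remains is a risk of uneven final follow-up.
- **A reader might infer that E.1 cannot be carried out at all.** This also goes too far. The regimen ends before surgery, and the day-of-procedure visit lets both arms be asked about the local reactions listed in D.6. C.7 tells patients to report side effects, and E.3 gives a 24/7 line for any adverse event. C.2 is headed as study visits and includes the call, so the word visit could be read broadly. Still, self-report is not the active inquiry that E.1 describes, and no adverse-event question is attached to the call.
- **A reader might infer a two-fold difference between arms, with 92.5% of patients never asked after surgery.** Both figures treat confirmed infections as if they were the visits. The trigger is symptoms or a worrying photograph, so each is the extreme of a range.

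**Conclusion.** The point holds as a contradiction between stated follow-up rules, together with a mismatch between E.1 and the contact schedule. Three groups are named for one contact, and active adverse-event inquiry after surgery depends on suspected infection.

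If the hypothesis is true, that inquiry may be more frequent in controls. The size cannot be fixed from the document. The ratio is at most 2 under the model above and about 1.2 to 1.3 if 10% to 20% of uninfected patients are also seen. This rests on the planning rates of 10% and 5%, on every infected patient being seen, and on uninfected patients being seen equally often in both arms.

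The consequence is small. Reactions to the pre-operative regimen can be asked about on the day of the procedure, and self-report is open to all. No sample size, test or estimate changes. It is a cheap improvement and not a threat to the trial's main conclusion.

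**What to change.** Reconcile C.1, C.2 and the Appendix with D.6.1, so that every enrolled subject in both arms is contacted once at one month, whether or not an appointment was needed or an infection found. State in E.1 that this contact counts as a study visit, and put the adverse-event and serious-adverse-event question into the call script next to the existing questions on infection and the surgical site.

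The cost is one more question per call, plus extra calls that depend on the rule now followed:

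- relative to C.2 and the Appendix: about 64 (42.4 + 21.2 = 63.6 at the planning rates);
- relative to C.1: one for every patient seen for suspected infection, so about 142 if 10% of uninfected patients are seen (80.6 + 61.5) and about 220 if 20% are (118.7 + 101.8);
- relative to D.6.1: none.

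The downside is staff time.

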
I. Appendix

Screening	Patient will be identified as a potential research subject. Their chart will be flagged for their pre-operative visit..
Pre-operative visit	During their standard pre-operative visit, the physician will inform the patient of the study. If the patient agrees to participate, a link to REDCap or a physical copy of the consent form will be sent to them. Patients will be placed into one of two arms. They will be given instructions on the pre-operative decolonization if they are placed in the experimental group.

Day of procedure	Patient will come in for their procedure. They will fill out the demographic survey and receive a hard copy of their consent form.
Post-operative management	Patients will send a picture of their surgical wound to the physician 2 weeks after and 4 weeks after their procedure. If the patient does not develop any infection, they will be called 1 month after their procedure to check on their progress.
Infection develops	Patients will be asked to report to the office. A swab will be taken of the infection site to test for the causative pathogen. Appropriate treatment will be given when the results are received.
